## **Serious Adverse Events**

A serious adverse event (SAE) is defined as any event occurring during the clinical trial that results in death or significant deterioration in health, including life-threatening illness or injury, permanent impairment of body structure or function, hospitalization or prolonged hospitalization, or the need for medical intervention to prevent permanent impairment. Events resulting in fetal distress, fetal death, congenital anomaly, or birth defect are also included.

The following hospitalizations are not to be recorded or reported as SAEs: hospitalizations for diagnosis or elective treatment of preexisting conditions, hospitalizations for insurance reimbursement, planned hospitalizations or elective surgeries not related to an adverse event, or admissions for comprehensive physical examination.

## **Reporting Procedures**

If a serious adverse event occurs during a medical device clinical trial, the investigator must immediately take appropriate treatment measures for the subject. At the same time, the investigator must report the serious adverse event to the clinical trial institution management department and the ethics committee within 24 hours of becoming aware of the event. The investigator is also responsible for following up on the serious adverse event according to the clinical trial protocol and submitting a follow-up report regarding the event.

## **Provisions on Protocol Deviations and Amendments**

### **Protocol Deviations**

Clinical trials must adhere to the protocol approved by the ethics committee; any intentional or unintentional conduct that deviates from the protocol is referred to as a

protocol deviation.

According to the responsible party, protocol deviations can be classified into deviations due to non-compliance by the trial institution and deviations caused by subject non-compliance. According to severity, deviations can be categorized as minor or major protocol deviations. Major deviations have one or more of the following attributes: impacting the safety and rights of the subject; affecting the subject's willingness to continue participation; or compromising data quality and integrity. Minor deviations generally do not have these three attributes.

Minor protocol deviations are usually reported periodically to the ethics committee, and investigators must explain the reasons, impact, and measures taken. Major protocol deviations should be reported promptly.

Each protocol deviation should be followed up with corrective or preventive measures to address the error and prevent recurrence of similar deviations.

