## **Analysis Populations**

Statistical analyses will be based on clearly defined analysis populations prior to data analysis in this study:

**Full Analysis Set (FAS):** The set constructed according to the intention-to-treat principle, including all subjects who participated in the study and received TAR+FET treatment.

**Per Protocol Set (PPS):** A subset of FAS, including all subjects who completed the trial without major protocol violations.

Baseline data will be analyzed based on the FAS, and analyses of primary and secondary outcomes will be performed on both FAS and PPS.

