## **PPS Exclusion Criteria**

(1) Subjects who violated selection criteria (did not meet inclusion criteria or met exclusion criteria), and such violations substantially affect efficacy or safety assessment;

(2) Subjects in Experimental Groups 1 or 2 (arch clamping combined with bilateral cerebral perfusion) who, for any reason, are switched intraoperatively to conventional TAR+FET (control group) treatment.

In addition to the above criteria, any other conditions that may affect assessment of efficacy or safety will be determined by investigator discussion on a case-by-case basis.

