### **Statistical Analysis Content**

### **Trial Completion Status**

List the total and per-center numbers and proportions of screened subjects, screening failures, and the reasons for screening failures.

Calculate the numbers and proportions of subjects enrolled, who completed the trial, and who withdrew early, including reasons for withdrawal.

Summarize protocol deviations according to the type and severity.

Provide a detailed subject population breakdown in tabular form.

Present a subject disposition flowchart, including detailed reasons for screening failures.

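### The per-protocol set drops major violations without defining them; the only definition of major is impact-based and written for ethics reporting, so membership can come to depend on the primary outcome

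*Combined protocol and SAP*

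**What the plan says.** All quotations are from the combined protocol and SAP.

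- **Analysis Populations** defines the PPS as "A subset of FAS, including all subjects who completed the trial without major protocol violations". Primary and secondary outcomes are analysed on both FAS and PPS. Neither set is named as decisive.
- **PPS Exclusion Criteria** names two grounds. One is an eligibility violation, provided that "such violations substantially affect efficacy or safety assessment". The other covers Group 1 or 2 patients who "are switched intraoperatively to conventional TAR+FET (control group) treatment". Any other condition that may affect the assessment of efficacy or safety goes to investigator discussion, case by case.
- **Protocol Deviations** is the only place that says what makes a departure major. It gives three alternative attributes, and the list begins: "Major deviations have one or more of the following attributes: impacting the safety and rights of the subject". The other two concern whether the patient still wants to take part and whether the data remain sound. The use made of the grade there is reporting to the ethics committee: "Major protocol deviations should be reported promptly".
- **Trial Completion Status** brings severity into the statistical section, for description only: "Summarize protocol deviations according to the type and severity".
- **Primary Outcome Measures** makes the endpoint a composite of death, RRT, stroke and paraplegia. The rationale for the design says that neither researchers nor participants can be blinded.

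**The concern.** Membership of an analysis set should not depend on the outcome being compared. Every component of the composite is a harm to the patient. If a deviation is graded by the harm that followed it, a departure followed by a stroke tends to be graded major, and the same departure in a patient who recovers tends to be graded minor. The first patient leaves the PPS and the second may stay.

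Case-by-case discussion opens the same route without any grade, because the investigators know the allocation and can know the outcome. No outcome-masked review is described, and no freezing of the PPS before lock (Database Lock asks only for two signatures).

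Both primary tests are run on the PPS. Test 1 is superiority of Group 1 over control; test 2 is non-inferiority of Group 1 to Group 2 with a 5-point margin. Selective removal of event patients in Group 1 favours both claims, and removal in the comparator works against them.

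**Working it through.** **1. The plan's own figures (context; none is disputed).** For 13% vs 30%, one-sided 0.025, 80% power, pooled formula with mean rate 0.215:

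n = [1.960·√(2·0.215·0.785) + 0.842·√(0.13·0.87 + 0.30·0.70)]² / 0.17² = 90.5, so 91, as stated.

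For test 2 (13% vs 25%, margin 5%), the unpooled formula gives 82 and Farrington-Manning 85, against the stated 84. Dropout: 91/0.90 = 101.1, so 102 per group and 306 in total.

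**2. Reading the sections together.**

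| Question | What the text gives |
|---|---|
| Is major defined for the PPS? | No |
| Is it defined elsewhere? | Once, by impact, for ethics reporting |
| Is that grade said to decide the PPS? | No |
| Are the PPS exclusions a closed list? | No; two grounds, then investigator discussion |
| Is there a masked or pre-lock step? | None described |

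So the PPS rule is either undefined or, if the only available definition is borrowed, linked to what happened to the patient.

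**3. Illustration of size.** Assumptions, none given by the documents: a fraction d of an arm has a deviation, independent of outcome; every patient with both a deviation and an event is removed; every patient with a deviation and no event is kept. This is the extreme removal rule. The interval is Wald 95% (the plan names no method), with 92 per arm (102 × 0.90 = 91.8). A true rate p becomes

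PPS rate = p(1 − d) / (1 − dp).

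*Test 2 at the margin, true rates 25% (Group 1) and 20% (Group 2), true difference 5.0 points:*

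- d = 20% / 5%: 0.20/0.95 − 0.19/0.99 = 0.2105 − 0.1919 = 1.9 points
- d = 20% / 10%: 0.2105 − 0.18/0.98 = 2.7 points
- d = 20% / 20%: 0.2105 − 0.16/0.96 = 4.4 points
- d = 5% / 20%: 0.2375/0.9875 − 0.1667 = 7.4 points

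*Test 1 with no true effect, 30% in both arms:*

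- d = 20% / 5%: 0.24/0.94 − 0.285/0.985 = −3.4 points
- d = 20% / 10%: 0.2553 − 0.27/0.97 = −2.3 points
- d = 20% / 20%: 0

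False-positive rates on the PPS, from 400,000 simulated trials per scenario (about 2.7% with no removal, for both tests):

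| Deviations, Group 1 / comparator | Test 2 | Test 1 |
|---|---|---|
| 20% / 5% | 8.0% | 7.7% |
| 20% / 10% | 6.1% | 5.6% |
| 20% / 20% | 3.4% | 2.6% |
| 10% / 10% | 3.0% | not tabulated |
| 5% / 5% | 2.8% | not tabulated |
| 5% / 20% | 1.0% | 0.7% |

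Two variations on these scenarios:

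- If half of the deviations without an event are also graded major, the 8.0% and 6.1% for test 2 fall to 5.0% and 4.3%.
- If FAS and PPS must both pass, the false-positive rate does not exceed 2.7% in any scenario.

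A normal approximation at another boundary (30% vs 25%, 91 per arm, deviations in Group 1 only) gives 3.6%, 5.1% and 10% for d = 5%, 10% and 20%, against a nominal 2.5%.

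**The case against.** A reader might infer that the plan contains a written rule that removes the harmed patient and keeps the unharmed one. The documents do not support that.

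- No section says that the reporting grade decides the PPS. One section speaks of deviations, the other of violations, and the PPS has its own exclusion section. Neither of its two named grounds is defined by harm to the patient.
- An impact on safety and rights can mean the kind of deviation, or its potential, rather than harm that occurred.
- The data-quality attribute can make a deviation major with no harm at all, so an unharmed patient is not always kept.

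A reader might also take 6-8% as the expected error rate. It is not. It needs unequal deviation rates, worst-case removal, and the PPS alone carrying the claim. A large gap between Groups 1 and 2 is hard to presume, since both use the same arch-clamping operation. Switches to the control procedure are excluded whatever the outcome, which shrinks the remaining pool. The model also treats deviations as unrelated to outcome, and such a deviation did not itself affect safety. It therefore shows what a crude after-the-event grading would do, not what the definition requires.

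All of this stands, and it limits the size and certainty of the point. It does not supply the missing definition. Nor does it answer the open-ended investigator decision, which lets outcome influence membership without any link to the reporting grade.

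**Conclusion.** The point holds as a gap with a possible bias, not as a demonstrated one. What makes a violation major is undefined for the PPS. The only definition available is impact-based and written for another purpose, and the remaining exclusions rest on unmasked case-by-case judgement. PPS membership can therefore depend on the primary event.

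Direction and size cannot be determined from the documents. Under the worst-case removal rule, equal deviation rates do little: 3.4% for test 2 at 20% in each arm, and no inflation of test 1. An assumed excess in Group 1 gives about 6-8%, and the reverse imbalance gives 1% or less. Only the PPS analysis is exposed. The consequence depends on which set decides, which the plan leaves open; this matters most for the non-inferiority test. The change is worth making because it is cheap and better than the stated rule, not because a large error has been shown.

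**What to change.** In Analysis Populations and PPS Exclusion Criteria:

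1. State that the minor/major grade under Protocol Deviations is for ethics reporting and does not determine the PPS.
2. Define PPS-excluding deviations as a fixed list by type of act, not by consequence (for example, allocated operation not performed, or eligibility criterion not met at randomisation). Apply it identically to all three arms, in place of case-by-case discussion.
3. Apply the list before database lock, from a listing that hides outcomes.

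The cost is a few sentences and one masked listing, with no new data and no extra patients. The PPS may become slightly larger or smaller than under the present wording.

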## Measures to Control Protocol Deviations

### Sponsor

(1) The protocol should be written in clear language and designed in such a way as to minimize the possibility of protocol deviations; potential deviations should be easy to detect and identify.

(2) During investigator meetings, special training should be provided regarding protocol implementation details and the reporting and monitoring of protocol deviations.

(3) Deviation records should be reviewed periodically to identify trends and systemic errors; corrective actions must be carried out for identified deviations. If immediate protocol or study plan amendments are necessary, the study project should be suspended until correction and retraining are completed.

### Investigators

(1) During the project evaluation stage prior to study initiation, investigators

should carefully read the protocol and thoroughly discuss its feasibility at their institution with the sponsor.

(2) During the informed consent process, investigators should explain the importance of protocol adherence to subjects, detail the protocol and trial requirements, and highlight important procedures and follow-up matters.

(3) Investigators must comply with the protocol approved by the ethics committee and must immediately document and explain any deviations if they occur.

## **Subjects**

During the signing of the informed consent form, investigators should explain in detail the requirements of the protocol and highlight important examinations and follow-up matters.

## **Retraining**

Investigators must undergo retraining (and, if necessary, multiple retraining sessions) in the following situations:

- (1) Misunderstanding of the protocol occurs;
- (2) New investigators join the study;
- (3) The research plan is changed;
- (4) Reminders are needed regarding protocol details.

## **Reporting Protocol Deviations**

The principal investigator must regularly report the progress of the medical device clinical trial to the ethics committee and promptly report any events affecting participant rights and safety or any protocol deviations.

If, in order to protect the subject's rights, safety and health, a deviation occurs in an emergency situation and cannot be reported in a timely manner, it must be reported as soon as possible afterwards in writing according to relevant regulations.

If the clinical trial protocol, informed consent, or other files are to be revised, or

if a previously suspended clinical trial is to be resumed, written approval from the ethics committee must be obtained before continuing the trial.

Investigators must strictly adhere to the clinical trial protocol; no deviation or substantive change is permitted without approval from the ethics committee. However, if immediate action is required to eliminate a direct hazard to subjects, a written report should be submitted afterwards.

## Protocol Amendments

If, during the trial, investigators believe that the protocol is flawed (e.g., inclusion/exclusion criteria do not cover the target population, difficulty enrolling cases, or sample size does not match clinical reality), the protocol should be amended and submitted to the ethics committee for approval.

## Progress Schedule

Key Task	Timeline
Clinical Trial Initiation Meeting	May 2025 - June 2025
Ethics Committee Approval	May 2025-June 2025
First Subject Enrollment	June 2025
Last Subject Enrollment	May 2026
Completion of Follow-up for All Subjects	May 2027
Database Lock	May 2027
Completion of Final Report	June 2027

## Follow-up and Medical Measures After Completion of the Trial

After the end of the trial, subjects will no longer be followed up. Subsequent medical measures will be determined jointly by the investigator and the subject, based on actual clinical management of the disease.

## Responsibilities of Each Party

(1) Medical and Health Institutions: Bear primary responsibility for clinical research implementation, establish and improve the organizational, quality assurance, conflict-of-interest prevention, and subject right-protection systems for scientific,

standardized, and orderly clinical research, and ensure quality assurance and full-process management for clinical research.

(2) Institutional Office: Responsible for project review, process management, quality management, contract management, close-out, and file management of clinical research, and coordinate scientific and ethical reviews.

(3) Academic Committee: Comprised of relevant institutional leaders, functional department heads, and clinical research experts, responsible for scientific review of clinical research, including rationality, necessity, feasibility, research objectives, intervention measures, study hypotheses, methods, sample size, endpoints, and safety.

(4) Ethics Committee: Protects the rights and safety of subjects, with special attention to vulnerable populations. Reviews the scientific and ethical aspects of clinical trials throughout the entire process.

(5) Principal Investigator: The project leader participating in the clinical trial; responsible for drafting the protocol, initiating and managing the trial, and ensuring the scientific validity and ethical compliance of the study.

